Antenatal breastmilk expression from 34 weeks of gestation.

Safety in pregnancy and benefits for the newborn infant: protocol for a
pilot randomized study

The EXPRESSMOM Study

Background

The World Health organization (WHO) recommend exclusive breastfeeding to 6 month of age, and for up to 2 years of age along with introduction to solid foods (1). According to their data, only 38% of all children aged 0-6 months are exclusively breastfed. The 2025 goal for WHO is to increase the rate of exclusively breastfed infants aged 0-6 month to at least 50%. In Denmark, only 16.9% of infants are exclusively breastfed at 6 months, although between 97 – 99.5% initiate breastfeeding right after birth (2, 3).

Mother's own milk (MOM) is the best feeding option for all newborn infants, including those born preterm. Besides being a source of macronutrient nutrition, MOM is also a source of vitamins, minerals and bioactive components, such as growth factors, immunoglobulins, lactoferrin, antioxidants and cytokines. These bioactive components contribute, among others, to activate the immune system, mature the infant intestine and promote neurodevelopment (4). In addition, breastfeeding has benefits for both mother and infant. Breastfed children have a reduced risk for various diseases later in life e.g. cardiovascular and metabolic diseases and obesity (5-7). Furthermore, women who breastfeed seem to have a reduced risk for breast- and ovarian cancer, osteoporosis as well as diabetes later in life (7).

MOM is complex and changes throughout the lactation period and by that adapt to the current need of the infant (8). The first milk, colostrum, is very valuable and contains a high amount of fat, protein and bioactive components, important for the infant, compared to mature milk, which primarily content is carbohydrates. If MOM is not available right after preterm birth, the infant receives donor human milk (DHM) or infant formula (IF) depending on gestational age. Mothers who deliver preterm often have a delayed onset of lactation (9), and they do not produce enough MOM until several days after delivery. Therefore, the primary source for enteral feeding for the preterm infants the first days of life will be DHM. DHM is mature milk, and contains lower amounts of protein, fat and bioactive components.

We know that receiving MOM as primary enteral feeding is critical for preterm infants with regard to gut health (4), lowering risk of infections and improve neurological development, both during infancy and later in life (10), but the mothers are often struggling with breastfeeding establishment in the Neonatal Intensive Care Unit (NICU) due to environmental factors, stress and maternal disease or blood loss related birth.

A study from 2015 showed that if mothers of preterm born infants less than 32 weeks of gestation starts to express milk within an hour after delivery, they produce nearly twice the amount of milk during the first week after delivery compared to mothers who initiate breastmilk expression 1-6 hours after birth (11). The difference in milk volumes were also statistically significant in week 3 and 6 after delivery, although the

number of lactating women declines. Despite the low number of participants in the study, this indicates that early expression can enhance milk production and maybe accelerate the onset of lactogenesis.

Within the last couple of years, a rising interest is seen in expression and storage of breastmilk before birth (antenatal breastmilk expression = aBME), to ensure an exclusive mother's milk diet and enhance the process of lactogenesis. It has been a general concern that aBME, could induce preterm labor due to rising oxytocin levels. This does not seem to be the case: In a recent published randomized controlled trial by Forster et al (12), 635 pregnant women with diabetes were randomized to either start aBME from week 36 of pregnancy or standard care (no aBME). During the first aBME they were monitored with cardiotocography surveillance, and some women had increased uterine activity, but no episodes of tachysystole, hyperstimulation or preterm birth. These findings were evaluated by a safety committee and was not found to be a risk factor for the fetus or for preterm birth. The authors found no difference between the groups in the proportion of infants admitted to the NICU or gestational age at birth. Furthermore, they found no difference between the groups in birth characteristics (eg. Onset of labor, type of birth or blood loss). They conclude that their study indicates that it is safe to advise low risk pregnant diabetic women to express breastmilk from gestational age 36. In addition, a systematic review of breastfeeding (of siblings) during pregnancy, found comparable rates of preterm birth between breastfeeding pregnant women and non-breastfeeding pregnant women (13). Furthermore a randomized study from 2015 comprising 200 pregnant women found that starting aBME at term, shortened the time from initiation to full establishment of breastfeeding (14). Recently, Foudil-Bey et al. did a scoping review to evaluate aBME outcomes (15). They identified twenty articles eligible for the review. The initiation time of aBME differs among the included studies, with twelve of the studies expressing BM after week 36. Four studies recommend to start expressing BM between 32 and 36 weeks of gestation, two before week 32 and the remaining two studies did not specify the timing of aBME. The studies who recommend to start aBME before week 36 were old and weak in methodology. They conclude, that existing studies on aBME varies widely in objectives, target population, interventions and outcomes, and that higher quality studies with clear hypothesis and populations are needed to determine safety and efficacy of aBME.

A couple of studies also included in the review by Foudil-Bey et al, evaluated feedback from the women with regard to perception and experience with aBME. The negatives aspects were among others discomfort or pain during aBME, time or energy burden, anxiety about having insufficient colostrum supply and feeling of internal pressure to succeed. On the other hand, they reported a sense of ownership and confidence with breastfeeding after performing aBME. They had positive feelings about having done something for the

baby and had a feeling of preparedness by having collected colostrum ready for the first feed to the infant (12, 16-18).

On this background we hypothesize that antenatal breastmilk expression

- 1) is a safe procedure before week 36 of pregnancy
- 2) can ensure sufficient supply of MOM for the preterm infants immediately after birth
- 3) promotes feeding with exclusively MOM for preterm infants
- 4) has a positive effect on the mothers feeling of confidence and preparedness for breastfeeding

Objective

In this pilot study, we want to investigate if aBME from week 34 of pregnancy is a safe and feasible procedure for the mother and fetus. Furthermore as secondary outcomes, we want to evaluate breastfeeding rates and mother's experiences with aBME. The evaluation of the mothers experience with aBME will be a separate study conducting qualitative methods.

Methods:

Intervention

In a pilot randomized study, we will include 60 healthy pregnant women. We will allocate 30 women to start aBME from week 34+0 of pregnancy until delivery and compare them to 30 women who does not perform aBME. All women included in this study will receive standard care, and have an individual consultation with a breastfeeding trained midwife in week 33 of their pregnancy. The women allocated to the intervention group will besides breastfeeding consultancy, also be taught how to perform aBME and store breastmilk correctly during the midwife consultation. To detect any signs of uterine contractions or fetal influence a cardiotocography (CTG) will be performed in the intervention group before, during and after the first aBME. In total 40 minutes of CTG surveillance. If the CTG is unclear, it will be assessed by the obstetric doctor in charge of this study, [name] or a substitute. In case of pathological CTG, the women will be send to the obstetric emergency department for further assessment. If the CTG is normal the women in the intervention group can perform aBME 5 minutes from each breast two times per day from week 34 until birth, and collect and store any expressed milk. They will be provided with a schedule to register their aBME sessions (Please see attachment).

Participants will receive both written and oral information about the trial and the intervention group will in addition receive safe storage of MOM (please see attachment 1, 2) and be provided with the needed syringes and labels for expressed milk. Participants will be instructed to be aware of precautions

related to aBME such as: continuous excessive painful contractions, vaginal bleeding or decreased fetal movements. In case of such symptoms they have to contact obstetric emergency department. During the intervention and 8 weeks after birth the participating women will receive weekly push-messages through an application on their smartphone. The messages include short questions about the aBME as well as regarding feeding of the infant after birth. At the end of the study we want to evaluate the mothers experience with the study through an online questionnaire. The questionnaire will be submitted as a supplement to this protocol when finished. All data is managed through OPEN/REDCap and stored in a secure server ([OPEN - Open Patient data Explorative Network - forside \(rsyd.dk\)](http://OPEN - Open Patient data Explorative Network - forside (rsyd.dk)))

Trial design

Randomized pilot study with 1:1 into one of two arms: Group A aBME from week 34+0 or Group B no aBME. Randomization in this pilot trial will not be blinded to participants or investigators performing the data analysis due to the intervention.

Participants/Population

Participants are nulliparous pregnant women from the island of Funen who plan to give birth at Odense University Hospital. We intend to include 60 pregnant women, 30 in each group. If recruitment rate is low, we will widen the inclusion criteria and also include multiparous women who do not breastfeed siblings.

Inclusion criteria:

1. Healthy nulliparous women with no major chronic or pregnancy related diseases
2. BMI <27
3. Danish speaking
4. Singleton pregnancies
5. Planning to exclusively breastfeed their infants and deliver at Odense University Hospital (Odense and Svendborg)

Exclusion:

1. Suspected fetal intrauterine growth restriction or known major fetal anomaly
2. Women at risk of preterm birth with one of the following diagnoses: Placenta previa, premature preterm rupture of membranes (PPROM) or previous cervical conization
3. Women taking medications where breastfeeding is contraindicated
4. Women with prior breast surgery: Breast reductive surgery or breast implants

Ethical approval

Application for the Ethical Committee of Southern Denmark (project number: 86409) is done and the committee decided that no regional ethical approval is necessary in order to perform this study. The Research Ethics Committee of University of Southern Denmark has approved the study (Project ID: RECID281). All data collected will be entered and stored on a secure server in the Region of Southern Denmark, OPEN (www.open.rsyd.dk) and the project is approved by the Data Protection Agency at the Region of Southern Denmark. The study will be registered at clinicaltrials.gov.

Recruitment and information

[figure not shown]
Participants will be recruited using video and text announcing on social media and in outpatient/midwife clinics in the department of obstetrics. If the women are interested in participation, they click on a link and fill in an online document with contact information (telephone and email) and confirm that they comply with the inclusion criteria. After conforming their interest in participating, they receive written information about the trial (Appendix 1) through email. Following, primary investigator or others in the study group will contact them by telephone within 2-4 days to give oral information. Signed written consent will be obtained using E-Boks. Then randomization can be done and consultation in week 33 can be planned by the project-midwife by telephone.

Randomization

When the women have given informed written consent, they will be randomized to either group A (intervention) or B (control). Randomization will be done using a web-based randomization program (REDCap in OPEN). Baseline maternal characteristics, obstetric and neonatal will be obtained through medical records:

Maternal:	Neonatal:

• Age• Smoking• Medications• Prepregnancy BMI• Delivery mode	
• Gestational age at birth• Gender• Anthropometry at birth• APGAR scores at 1 and 5 min• Umbilical cord pH• Feeding mode if hospitalized

Figure 1: Overall study design

Time	28-32 weeks of pregnancy	33 weeks	34 weeks	36 weeks	37 weeks	Admission for birth	8 weeks post partum
ENROLLMENT							
Eligibility for study screen	✗						
Informed content and information on email	✗						
Randomization to either active aBME or no aBME	✗						
INTERVENTION							
Group A: Midwife consultation		✗					
Group A: aBME 10 min a day intervention group A			→				
Group B: Midwife consultation		✗					
Group B: no aBME			→				
DATA COLLECTION							
Demographic maternal data	✗						
							✗

Obstetric data from medical records								Figure 2:
Neonatal data from medical records	Enrollment	Post randomization (intervention?)			Post-partum			Detailed
aBME data, and infant feeding data (App-tracking)								schedule
Mother's experience with the intervention (questionnaire)								of

participant enrolment, intervention and data assessment

Figure 3: Gantt diagram of project main time schedule

Event	Time	2021		2022			2023			2024		
Protocol writing and approval												
Ethical approval												
Training of staff and recruitment video production												
Patient recruitment and randomization												
August. 2022 – August. 2023												
Intervention												
August 2022 – August. 2023												
Data collection and outcome analyze												
Article writing												
Publication												

Outcomes:

Primary outcome:

1. Gestational age at birth comparing the two groups

Secondary outcomes

1. number of weekly antenatal stimulations/expressions (aBME) before birth
2. number of women in intervention group capable of expressing any milk
3. breastfeeding rates 1, 2, 4, 6 and 8 weeks after birth comparing the two groups
4. number of exclusively breastfeeding versus partial breastfeeding in each group at 1, 2, 4, 6 and 8 weeks after birth

5. Contractions and/or fetal stimulation during aBME, assessed with CTG
6. Women's experience with the intervention (separate qualitative study)

Sample Size

In general the evidence in aBME is limited. A few prospective studies has been conducted, and only one larger RCT. This RCT included 635 participants, where aBME was performed from week 36 of pregnancy. They were not able to detect any difference in gestational age at birth or report any adverse events in relation to the aBME. Before the larger RCT they conducted a pilot study, which consisted of 43 participants. Our aim with this study is to primarily test safety and feasibility with the procedure aBME from week 34, and since no study has been done from this week of pregnancy, a reliable power calculation is not possible to make. Therefore we estimated that 30 participants in each group is a realistic and feasible number to include in the pilot study. To detect a difference in gestational age at birth based on 80% power, we estimated that we would need a total of 176 participants, 88 in each group (mean, SD, derived from Soltani et al(19)). If the pilot study shows no trend towards a higher proportion of preterm birth in the intervention group, we will proceed to the larger trial.

Data collection:

Demographic data on the mothers (maternal age, education level, ethnic background, parity and smoking status) will be obtained through medical files. Infant data on gestational age, complications such as preterm contractions or birth and feedings from birth, will be obtained from medical records after birth. To obtain data on aBME and breastfeeding rates after birth, we will use SMS tracking via an app based in the RedCap system. From intervention start until 8 weeks after birth participants in the intervention group will receive a weekly sms, with questions on how many times they stimulated and if they were capable of expressing any milk. The control group will receive a weekly message which regards if they have been giving birth, to be able to initiate the questions on breastfeeding. After birth questions will regard breastfeeding initiation. After eight weeks the mothers experience and evaluation on the study will be evaluated in an online questionnaire.

Data analysis and statistics:

Data will be collected in order to meet the CONSORT guidelines for Randomized Controlled Trials. Comparability of the two groups by intention to treat analysis. Where data are normally distributed, comparison of means will be done using unpaired t-tests. If data are not normally distributed a non-parametric test for unpaired data will be used, eg. Mann-Whitney test or permutation test. Multivariate

analysis will be carried out, if data shows differences in maternal or infant characteristics possibly affecting outcome.

[Interruption of the trial](#)

The involved investigators can stop the trial if the protocol is not followed or unexpected adverse effects in relation to the aBME such as contractions, vaginal bleeding or overrepresentation of preterm birth in the intervention group. The investigators in charge can pull out participants if they find it irresponsible to continue due to side effects or new pregnancy related conditions, where aBME could be contraindicated. Participants can at any time retract their consent and stop the intervention.

[Patient insurance](#)

This trial is covered by the Patient Compensation Scheme and Labour Market Insurance.

[Publication](#)

All results, positive, negative as well as inconclusive results will be published.

[Possible clinical implication:](#)

We expect this initiative to have positive impact on both mother and infant with improved breastfeeding rates and mothers confidence with breastfeeding. If aBME from 34 weeks does not induce preterm birth, we aim to investigate if this procedure is safe earlier in pregnancy and especially among pregnant women at increased risk of preterm delivery. In the long term, this could increase the number of preterm infants fed exclusively MOM and possibly contribute to improved gut health and neurodevelopmental outcome for preterm infants.

Referencer

1. WHO/UNICEF. Global nutrition targets 2025: breastfeeding policy brief (WHO/NMH/NHD/14.7). Geneva: World Health Organization; 2014.

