### 2.3 Intention to treat (ITT) and per protocol (PP) analysis

We will apply a modified ITT principle, considering only the participants who started the antenatal stimulation and/or participated in the breastfeeding consultation and as the ITT population. Participants who drop out before the breastfeeding consultation for any reason will not be included in any of our analyses. We consider PP as all of the participants who completed questionnaires until 8 weeks post-partum, no matter how well they complied with the intervention. We will apply ITT and PP analysis to our primary and secondary outcomes.

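### SAP 2.3 drops women lost between randomisation and the week-33 consultation from every analysis, so arm-related loss in that gap could bias the primary comparison

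*Protocol*

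**What the plan says.** **Order of events.** In the protocol (Recruitment and information; Randomization), a woman fills in an online form, is telephoned, and signs consent. Then: "Then randomization can be done and consultation in week 33 can be planned by the project-midwife by telephone". In the enrolment schedule, the row "Randomization to either active aBME or no aBME" is marked in the column "28-32 weeks of pregnancy", together with the eligibility screen and consent. The consultation is marked at 33 weeks for both groups. The Intervention section agrees: all women "have an individual consultation with a breastfeeding trained midwife in week 33 of their pregnancy", and for group A, "We will allocate 30 women to start aBME from week 34+0 of pregnancy until delivery".

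**Blinding.** Protocol Trial design and SAP 3.1 both say that participants and analysing investigators are not blinded.

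**Analysis set.** SAP 2.3 defines a modified ITT population as women who began stimulation and/or attended the consultation. It adds: "Participants who drop out before the breastfeeding consultation for any reason will not be included in any of our analyses". The per-protocol set requires completed questionnaires to 8 weeks. The protocol (Data analysis and statistics) names intention to treat and states no such restriction.

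**Related rules.**
- Protocol, Interruption of the trial: investigators may take a woman out for side effects, or for a new condition of pregnancy that could make aBME contraindicated.
- Protocol, Data collection: gestational age comes from medical records after birth.
- Protocol, Sample Size: a larger trial follows if the pilot shows no trend towards more preterm birth in the intervention group.
- SAP 3.4: reasons for withdrawal are registered in eight categories.

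**The concern.** Randomisation makes the two groups comparable at the moment of allocation. Removing women afterwards preserves that only if removal is unrelated to arm or unrelated to outcome. Here women can know their arm before the point at which SAP 2.3 begins to count them, so two routes to arm-related loss are open:

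- A woman may react to her allocation, whether disappointed to be a control or reluctant to express milk.
- Investigators may remove a woman whose new condition could contraindicate aBME. That ground bears mainly on group A, and such a condition may itself be linked to earlier birth.

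The second route is the more serious, because it could take women who will deliver early out of group A and leave their counterparts in group B. The primary outcome is gestational age at birth and is described as a safety outcome, so this would make aBME look safer than it is. No planned analysis would correct it, since neither the modified ITT set nor the per-protocol set brings these women back.

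**Working it through.** **1. Length of the gap.** Inputs: randomisation from 28+0 to 32+6 (schedule) and consultation from 33+0 to 33+6.
- Shortest: 32+6 to 33+0 = 1 day.
- Longest: 28+0 to 33+6 = 5 weeks 6 days.

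The consultation is the right end point because SAP 2.3 cuts there. Counting to the start of aBME at 34+0 would give 8 days to 6 weeks.

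**2. Preterm proportion.** Input: 30 women per arm (protocol, Participants/Population). One woman is 1/30 = 3.3 percentage points. The documents give no preterm rate. At an assumed 3% to 10%, the expected number per arm is 30 × 0.03 = 0.9 to 30 × 0.10 = 3.0. With so few events, one event removed from one arm can change the reading: 2/30 = 6.7% becomes 1/29 = 3.4%.

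**3. Scale for gestational age.** The plan's only sample-size figure is 88 per arm at 80% power for the larger trial. It cannot be reproduced, because the mean, SD and target difference are cited and not given. Solving backwards, with two-sided alpha 0.05 assumed and a normal approximation:

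d = √2 × (1.960 + 0.842) / √88 = 0.422 SD

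If a fraction L of group A is dropped, and those women deliver on average k SD earlier than the full group A mean, the remaining mean moves later by L × k / (1 − L). Both L and k are assumptions. With loss in group A only and k = 1:

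| Women lost | L | Shift (SD) | Share of 0.422 |
|---|---|---|---|
| 1 of 30 | 3.3% | 1/29 = 0.034 | 8% |
| 2 of 30 | 6.7% | 2/28 = 0.071 | 17% |
| 3 of 30 | 10% | 3/27 = 0.111 | 26% |

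At 3 of 30, k from 0.5 to 1.5 gives 0.056 to 0.167 SD, or 13% to 39%. These are shifts in means. SAP 4.2.1 plans medians and a rank-sum test, so the table gives a sense of scale and does not predict that test's result.

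**4. Precision.** At 0.422 SD, power is 37.3% with 30 per arm, 34.2% with 27 and 31.0% with 24. Loss that is balanced and unrelated to arm therefore costs only a little power. What is at stake is comparability.

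**The case against.** The strongest reply is that the cut-off is the same for both arms. Both attend a week-33 consultation, so the rule is formally symmetric, and equal loss unrelated to arm would shrink the sample without bias. No dropout rate or split by arm is given. All of this stands. It limits the point to a risk, but a symmetric rule does not produce symmetric loss when women can know their arm and one removal ground bears mainly on group A. The alternative way into the modified ITT set, starting stimulation, is also open only to group A. It should seldom matter, because expression is taught at the consultation.

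A reader might infer more than the documents support:

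- **That the losses are hidden.** They are not. SAP 3.4 registers reasons and the protocol commits to CONSORT. The women are missing from the analyses, not from the records.
- **That no rule covers women whose condition changes before week 33.** The protocol has a removal rule and SAP 3.4 has a category for removal in the participant's best interest. The fair criticism is that the protocol ties removal to aBME.
- **That eligibility rests on self-report alone**, because women "confirm that they comply with the inclusion criteria" online. The schedule has a screening row and there is a telephone call before consent. How eligibility is verified is not described, but that does not show that nothing is verified.
- **That randomising before week 33 is itself an error.** Group A's visit adds teaching, supplies and 40 minutes of CTG, and the midwife plans visits after allocation. Early allocation has a practical reason, so its timing is a trade-off.

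**Conclusion.** The point holds as a risk created by the analysis set, not as a demonstrated bias. The documents establish that allocation precedes the consultation by 1 day to just under 6 weeks, that women are not blinded, that SAP 2.3 discards every loss in that interval, and that the protocol's intention-to-treat statement carries no such limit. They do not establish that the analysed groups will differ from the randomised ones. That needs losses to occur, to differ by arm and to be related to gestational age.

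If they do, one woman is worth 3.3 percentage points of an arm. One to three early-delivering women lost from group A alone would move its mean by 0.034 to 0.111 SD towards apparent safety, given the assumed k = 1. Loss of such women from group B alone would push the other way. A change is worth making because it is cheap and the progression decision rests on very few events.

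**What to change.** Replace the SAP 2.3 sentence. Define the primary analysis set for gestational age at birth and preterm birth as all randomised women in their allocated arm, with birth data from medical records, unless a woman withdraws consent to use of her data. Keep the modified ITT set as a sensitivity analysis. Report losses before the consultation by arm, using the SAP 3.4 categories.

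SAP 2.2 must be worded to match. It treats stopping stimulation as withdrawal of consent and excludes controls who express. Those exclusions are a separate matter, but left as they stand they would undercut the new set.

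The cost is a little more record retrieval and slight dilution from women who never started the intervention; the sensitivity analysis will show how much. Randomisation need not move. Randomising at the consultation would close the gap for women not yet allocated, but SAP 3.5 says recruitment began on August 31, 2022. A mid-trial change would create two cohorts, and every slot would have to allow for a possible 40-minute CTG. It is an optional suggestion only.

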### 2.2 Adherence to the intervention

We consider all participants who answer weekly questionnaires until 8 weeks post-partum as full completers. E.g. if participants try to follow the intervention as well as possible, but do not stimulate the breast the recommended fourteen times a week, we will still consider them as completers of the study, if they have stayed in the study during the intervention and until eight weeks after birth. However, we will differentiate between study completion and intervention completion. Intervention completion is defined as participants who follow the intervention as well as possible until birth but do not answer all eight questionnaires. These participants will be included in the analysis for gestational age at birth, but will only be included in the breastfeeding analysis as long as they have answered the weekly questions. If participants do not want to perform stimulation anymore, we consider this as a withdrawal of consent. If participants are not adherent to the randomized group, e.g. they start to stimulate antenatal even though they are in the control group, we consider them as excluded from the study.

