#### Clinical features on infants

- Gestational age at birth (weeks+days)
- Gender (boy/girl)
- Birthweight (g)
- Birth length (cm)
- Head circumference (cm)
- APGAR score at 1 min (0-10)

- APGAR score at 5 min (0-10)
- Enteral Nutrition PP if hospitalized
- Way of feeding PP if hospitalized
- IV-solutions PP if hospitalized

Breastfeeding rates up to 8 weeks PP (both groups, weekly questionnaires):

- Feeding the first 24 hours (Did your child get anything other than your milk, yes/no)
- Are you breastfeeding (yes/no)
- If yes (Partially or exclusively breastfeeding)

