### 4.2.2 Secondary outcomes

#### Breastfeeding rates

- d)** Proportion of exclusively breastfeeding infants vs. partially breastfeeding in each group at 24 hours, 1, 2, 4, 6, and 8 weeks post-partum, will be analyzed with mixed effects logistic regression (with restricted maximum likelihood) and visualized by a bar plot.
- e)** Proportion of any breastfeeding infants vs. formula in each group at 24 hours, 1, 2, 4, 6, and 8 weeks post-partum will be analyzed with mixed effects logistic regression (with restricted maximum likelihood) and visualized by a bar plot.

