#### **4.5 Missing data**

Missing data will not be imputed. We will only use the data available.

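### Feeding is asked in each of the eight weeks after birth, but the comparative breastfeeding models leave out weeks 3, 5 and 7, so a change first reported then is lost to the model if the mother stops answering

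*Protocol*

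**What the plan says.** **Collection.** The protocol (Intervention) states: "During the intervention and 8 weeks after birth the participating women will receive weekly push-messages through an application on their smartphone". SAP 4.1 lists "Breastfeeding rates up to 8 weeks PP (both groups, weekly questionnaires" among the reported data. SAP 2.2 confirms the number when it describes women who "follow the intervention as well as possible until birth but do not answer all eight questionnaires".

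**Analysis.** Protocol secondary outcome 3 is "breastfeeding rates 1, 2, 4, 6 and 8 weeks after birth comparing the two groups", and outcome 4 is "number of exclusively breastfeeding versus partial breastfeeding in each group at 1, 2, 4, 6 and 8 weeks after birth". SAP 4.2.2 d) (exclusive versus partial) and e) (any breastfeeding versus formula) add a 24-hour point. Under d), the proportions "at 24 hours, 1, 2, 4, 6, and 8 weeks post-partum, will be analyzed with mixed effects logistic regression", and e) names the same times and the same model.

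**Incomplete answers.** Under SAP 2.2, women who do not answer every questionnaire "will only be included in the breastfeeding analysis as long as they have answered the weekly questions". SAP 4.5 adds: "Missing data will not be imputed. We will only use the data available". The per-protocol set in SAP 2.3 requires answers up to week 8, so a woman who stops earlier is outside it.

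**The concern.** The trial will hold answers from weeks 3, 5 and 7 that its comparative models do not see. If a mother keeps answering, little is lost, because a lasting change appears at the next modelled week. The difficulty is the mother who first reports stopping or partial feeding at week 3, 5 or 7 and then answers no more. Her last modelled answer is at week 2, 4 or 6, still in the earlier state, and no rule carries the later answer forward.

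A likelihood-based mixed model tolerates dropout that depends on answers it contains. Here dropout may depend on an answer the model has not been given. Missingness that would be at random given all weekly answers is then not at random for the fitted model. At stake is some upward bias in the modelled feeding rates. If change or silence differs between arms, the comparison is affected too.

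**Working it through.** The documents give no figure to reproduce on this point, so the check sets the two schedules side by side and then sizes the effect under stated assumptions.

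**1. Unused answers.** Collected: weeks 1 to 8. Modelled: 24 hours and weeks 1, 2, 4, 6 and 8. Not modelled: weeks 3, 5 and 7, which is 3/8 = 37.5% of weekly answers. With 60 women (Protocol, Participants/Population) that is 60 × 3 = 180 of 60 × 8 = 480.

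**2. Women affected.** Assume a constant weekly probability h of a lasting change, and a probability q of falling silent straight after first reporting it. The expected number whose change is never modelled is

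60 × q × h × [(1−h)² + (1−h)⁴ + (1−h)⁶].

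- h = 0.05, q = 0.3: 60 × 0.3 × 0.05 × (0.9025 + 0.8145 + 0.7351) = 2.2 women.
- h = 0.02 to 0.10, q = 0.05 to 0.50: 0.2 to 6.0 women of 60, or about 2% to 19% of all changes.

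**3. Assumed feeding curve.** The protocol Background gives 97% to 99.5% initiating breastfeeding and 16.9% exclusive at 6 months. Taking 98% as the start and a constant hazard over 26 weeks, the weekly hazard is −ln(0.169/0.98)/26 = 0.0676, so the weekly probability of loss is 1 − exp(−0.0676) = 0.0654. This joins an initiation rate to an exclusive-feeding rate, so it is only illustrative.

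With an assumed 10% weekly return to exclusive feeding, the long-run level is 0.10/(0.10 + 0.0654) = 0.605. True exclusive feeding at week 8 is then 0.605 + (0.98 − 0.605) × (1 − 0.1654)⁸ = 0.605 + 0.375 × 0.235 = 0.693, or 69.3%.

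**4. The planned type of model.** Random-intercept logistic models with categorical time were fitted to large simulated samples in which a given share of women fall silent after reporting a loss. Estimated week-8 exclusive feeding against the true 69.3%:

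| Silent after a loss (assumed) | Planned times | All weeks | Excess, planned | Excess, all weeks | Gain from all weeks |
|---|---|---|---|---|---|
| none | 69.8% | 70.6% | 0.5 | 1.3 | −0.8 |
| 25% | 71.4% | 70.4% | 2.1 | 1.1 | 1.0 |
| 50% | 73.5% | 70.6% | 4.2 | 1.3 | 2.9 |

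Repeat runs moved these figures by a few tenths of a point. Because the inputs are assumed, I carry the excess forward as roughly 2 to 5 points and the gain as about 1 to 3. With no silence, using all weeks gives no gain. About 1 point of excess remains even with all weeks.

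**5. If stopping is permanent.** With no return, true week-8 exclusive feeding is 0.98 × exp(−8 × 0.0676) = 57.1%. At 50% silence, two separate fits gave 60.1% and 63.9% from the selected weeks, and 56.2% and 55.7% from all weeks. The direction is the same, but the random-effect standard deviation ran to its upper bound. The random-intercept model is unstable in this case, and these figures are only approximate.

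**6. What does not change.** Among week-8 responders, the observed proportion was about 73.5% (25% silent) or 78.4% (50% silent) under the step 3 assumptions. It is the same whether or not weeks 3, 5 and 7 are used, because the silent woman is missing at week 8 either way.

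**The case against.** The strongest case on the other side is that selected time points were prespecified, that protocol and SAP agree on the post-partum weeks, and that these are secondary outcomes in a 60-woman pilot aimed at safety and feasibility. All of that stands and limits the weight of the point.

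Three stronger readings are tempting, and the documents do not support them.

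- *A reader might infer that the week 3, 5 and 7 answers are thrown away.* SAP 4.1 lists the weekly feeding data and reports categorical data as counts and percentages, so those weeks can be described. They are missing from the comparative models only.
- *A reader might infer that leaving out these weeks biases every reported breastfeeding rate.* Observed responder proportions, such as those a bar plot would show, are the same either way. Their larger problem is silence after stopping combined with no imputation, and this fix does not cure that.
- *A reader might size the effect with a life table.* With permanent stopping, a product-limit estimate from the five weeks gives about 60% or 63% (25% or 50% silent) against a true 57%. Neither document plans that estimator, so those figures do not describe the planned analysis.

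The inputs are also weak. The feeding figures are national, whereas these women plan to breastfeed exclusively and all receive a consultation. No source in the documents gives the silence rates, and the title of protocol reference 2 reports high participation with weekly texting. The effect may therefore be near the low end. No size was worked out for any breastfeeding (item e).

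SAP 2.2, which keeps women in while they answer weekly, might be read as implying that every answer is used. SAP 4.2.2 names the modelled times, however, and nothing says they are only reporting points. The analysts are unblinded (SAP 3.1), so this should be settled in writing beforehand.

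**Conclusion.** The point holds in a limited form. Three of the eight weekly answers enter no comparative model, and no rule brings them in. The consequence depends on women falling silent after reporting a loss. If 25% to 50% do, with some return to exclusive feeding, the planned type of model overstates week-8 exclusive feeding by roughly 2 to 5 percentage points, and using all weeks removes about 1 to 3 of them. These rates are assumptions, and without such silence there is no gain in bias.

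A reader might go on to infer a biased treatment comparison. The documents do not show one: similar silence in both arms moves both rates the same way, and distortion arises mainly if change or silence differs by arm. Open-label allocation makes a difference possible, but no differential scenario was calculated. This is a cheap improvement to a secondary analysis, and it does not touch the primary outcome.

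**What to change.** - In SAP 4.2.2 d) and e), fit the models to the 24-hour answer and all eight weekly answers, and keep 24 hours and weeks 1, 2, 4, 6 and 8 as the reporting points.
- Add a weekly discrete-time analysis of first change as a sensitivity analysis, because a random-intercept logistic model fits poorly if stopping is close to permanent.
- State in protocol secondary outcomes 3 and 4 that all weekly answers are used for estimation.

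The cost is wording in two documents, slightly more analysis work, and a model with more time terms in a 60-woman pilot. The answers are already collected, so there is no new data item and no added burden on participants.
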